The first cohort of five participants will complete the tele-health mCM intervention and provide evaluative feedback during an in-depth interview administered at the end of the study, and described in the Measures section below. A coding scheme will be developed for categorizing comments made during the interview based on the study components (e.g., mCM procedures, CBT, interface with smart phone app), subcomponents (e.g., mCM feasibility, CBT burden), and the evaluations drawn (e.g., CBT session too long, video upload still unclear after mCM training).

Successive Cohort Design Stage 2: Treatment Refinement

After the intervention and study have been modified based on information learned from the first cohort, we will treat a second cohort ($n = 5$). Though qualitative data will be evaluated and utilized using methods similar to those of the first cohort, the second cohort will more closely evaluate quantitative data. We will explore relationships of sociodemographic, baseline substance use, and psychiatric comorbidity variables with treatment retention and outcomes. This will identify treatment components to modify or enhance to maximize treatment effectiveness.

Successive Cohort Design Stage 3: Pilot Trial

After treatment modifications from cohort 2, we will conduct a pilot randomized controlled clinical trial. The primary goal of the trial is to evaluate the efficacy of a combined tele-health mCM intervention. The pilot trial will use a two-group design in which 45 participants with an AUD who smoke regularly will be randomized to either:

TELE-HEALTH MOBILE CONTINGENCY MANAGEMENT (mCM) INTERVENTION, a proactive tele-health intervention that combines evidence-based telephone CBT for alcohol and smoking cessation, a tele-medicine clinic for access to nicotine replacement therapy (NRT), and intensive CM therapy administered *via* a smart-phone based application (CM).

OR

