Three study visits (screening visit, end-of-treatment, and six-month follow-up) will occur at Duke-leased space at Hock Plaza, and the others will occur via telephone. Once a participant reports to the laboratory to begin the study, the study staff member obtaining consent will explain the study in detail, provide the participant with an IRB-approved written consent form explaining the procedures and risks, and answer any questions. The initial consent process and documentation takes place in a quiet, private office at Hock Plaza, and participants are given the chance to thoroughly read the consent prior to participation. Participants are given a copy of the signed informed consent form, and are given phone numbers to call if they have additional questions about the consent form or the research, if they have any problems during the study, or

if they have questions about participating in research studies in general. No study procedures will begin until informed consent has been obtained.

Participants

Participants will be eligible for inclusion in the study if they meet the following criteria:

- currently meet criteria for DSM-5 alcohol use disorder (meeting 2-8 criteria for AUD)
- have been engaging in hazardous drinking over the past month, defined as either exceeding a mean of 14 standard drinks/wk for men, 7 drinks/wk for women; or by consuming ≥ 5 on at least one occasion in the last month for men, ≥ 4 drinks on at least one occasion in the last month for women
- currently smoke at least 7 cigarettes per week
- can speak and write fluent conversational English
- are between 18-80 years of age
- are willing to make an attempt to quit both alcohol and smoking

Participants will be excluded from the study for the following:

- are expected to have unstable medication regimen during the study
- are currently receiving non-study behavioral treatment for alcohol use disorder or smoking
- have alcohol use disorder that exceeds our severity threshold of 8 symptoms or exhibit significant risk for alcohol withdrawal.
- have AUD that is in early remission, with no symptoms evident over the past month
- have experienced myocardial infarction in past 6 months
- contraindication to nicotine replacement therapy with no medical clearance to participate in the study
- use other forms of nicotine such as cigars, pipes, or chewing tobacco
- are currently pregnant
- have a primary psychotic disorder or current manic episode

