Prior to study entry, potential participants will complete a screening visit, including informed consent, the diagnostic interview, breath samples to assess alcohol and CO level, symptom self-report measures, alcohol and smoking history, mental health treatment history, and sociodemographic data. Participants will complete the Structured Clinical Interview for DSM-IV (First, Spitzer, Gibbon, & Williams, 1994) to diagnose AUD and psychiatric comorbidities. Urine samples will be obtained to screen for illicit drug use. Because urine drug screen results are not exclusionary, but rather provide descriptive information about the study population, any participant may refuse to provide a urine sample for drug screen purposes. We have not added this caveat to the informed consent form because we want to encourage participants to provide the urine samples. At any time, if a participant refuses to provide a urine sample, this will be documented as a protocol deviation. Of note, to date we have had no participants in studies in the Traumatic Stress and Health Research Laboratory refuse to provide a urine sample for drug screening. Urine drug screen results are collected on the participants' screening cover sheet in their research folder, and then are entered into a password protected database that is stored on the Duke psychiatry protected server; this database contains only deidentified data. Because the study drugs are each Category C drugs, urine pregnancy tests will also be completed for women of childbearing potential. We have developed a short interview for female participants; this interview will help us determine which female participants must have a urine pregnancy test, and when the test should be done. Female participants of childbearing potential who are not pregnant must agree to use appropriate contraception during the course of the study, and to notify study staff if they become pregnant during the study. Breath alcohol level (BrAC) will be assessed and must be 0.0 to continue with the screening.

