Descriptive statistics will be used to summarize all study variables. For continuous variables, means, standard deviations, percentiles, ranges, box plots and histograms will be generated. For categorical variables, frequencies and proportions will be generated. We will construct individual and mean trajectory plots of the longitudinal outcome variables to understand their general trends over time (i.e., post-treatment, 6 weeks and 6 months). Differences in treatment outcomes will be tested via generalized linear modeling. In addition, we will explore the variability and correlation structure of longitudinal variables. We will examine all variables to determine if parametric distributional assumptions (e.g. normality for the continuous variables) are valid. Variables not meeting distributional assumptions will either be transformed or modeled

using nonparametric or semi-parametric methods (e.g. quasi-likelihood methods). In planning a full RCT of the tele-health mCM intervention for AUD and smoking, it is important to evaluate study feasibility and treatment procedures, as well as gain information about effects on proposed outcome variables.

Specific Aim 1: Develop a multi-component alcohol and smoking tele-health mCM intervention.

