We will additionally explore differences in alcohol and smoking abstinence outcomes by treatment. Because the tele-health only intervention is expected to have a uniformly small impact on alcohol and smoking outcomes in comparison to the tele-health mCM intervention, implementation of an imbalanced-samples design, with twice as many participants randomized to the tele-health mCM treatment as to the tele-health only treatment, should maximize power for identifying treatment effects. That said, the proposed sample has 80% power to detect a treatment effect equivalent to Cohen's $d = 0.76$. For reference, in our pilot study of 22 smokers with PTSD, tele-health mCM yielded an effect size of Cohen's $d = 0.79$ at the 3-month follow-up. In particular, comparisons by treatment at post-intervention, 6 week follow-up, and 6-month follow-up will be made regarding alcohol consumption (drinks/week, number of heavy drinking episodes, proportion of days abstinent, and achieving recommended drinking limits) and smoking (number of cigarettes smoked each day and number of days of smoking abstinence) *via*

generalized linear modeling, which can accommodate normally and non-normally distributed (e.g., count) variables.

References

- Acuff, S. F., & Murphy, J. G. (2017). Further examination of the temporal stability of alcohol demand. *Behavioural Processes, 141*, 33-41. doi:10.1016/j.beproc.2017.03.020.
- Alessi, S. M., & Petry, N. M. (2013). A randomized study of cellphone technology to reinforce alcohol abstinence in the natural environment. *Addiction, 108*(5), 900-909. doi:10.1111/add.12093
- drinking outcomes in clinical trials. *Journal of Studies on Alcohol, 61*, 55-63.
- Bechara. A., Damasio, A.R., Damasio, H., Anderson, S.W. (1994). Insensitivity to future consequences following damage to human prefrontal cortex. *Cognition, 50*, 7-15.

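### The exploratory arm comparisons of drinking and smoking include no baseline value although baseline measures are collected; adjusting drinks/week and cigarettes/day is a cheap, optional precision gain of unknown size.

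*Combined protocol and SAP*

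**What the plan says.** The Data Analyses section states the method in general terms: "Differences in treatment outcomes will be tested via generalized linear modeling". Specific Aim 2 gives the comparisons exploratory status ("We will additionally explore differences in alcohol and smoking abstinence outcomes by treatment") and then lists them: "comparisons by treatment at post-intervention, 6 week follow-up, and 6-month follow-up will be made regarding alcohol consumption" and smoking. There are four alcohol outcomes (drinks per week, heavy drinking episodes, proportion of days abstinent, staying within recommended limits) and two smoking outcomes (cigarettes per day, days of smoking abstinence). The model is described only as "generalized linear modeling, which can accommodate normally and non-normally distributed (e.g., count) variables". No baseline covariate is named in either place.

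Baseline information is nevertheless collected:

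- Smoking-Related Measures puts cigarettes per day in the baseline smoking history questionnaire.
- Table 2 schedules the AUDIT at baseline.
- Consent and Screening Procedures lists "alcohol and smoking history, mental health treatment history, and sociodemographic data".
- The inclusion criteria under Participants require drinking to be assessed, since one route to eligibility is "exceeding a mean of 14 standard drinks/wk for men, 7 drinks/wk for women". The other route is a single heavy occasion: "or by consuming ≥ 5 on at least one occasion in the last month for men".

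For cohort 2, Stage 2 of the successive cohort design says "We will explore relationships of sociodemographic, baseline substance use, and psychiatric comorbidity variables with treatment retention and outcomes". That treats baseline use as a correlate of outcome, not as an adjustment term in the randomised comparison.

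**The concern.** Where an outcome has been measured in the same people before treatment, putting that value in the model removes variation that has nothing to do with treatment. With 45 randomised and only 15 in the comparison arm, precision is scarce. Data Analyses says that the pilot should yield information on outcome effects for planning a full trial, so the width of these intervals matters even though the comparisons are exploratory. Naming the covariate in advance also prevents it from being picked after the outcomes are known.

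**Working it through.** **Inputs.** From the documents: 30 v 15 randomised (Objectives; Participant Recruitment) and d = 0.76 (Specific Aim 2). Assumed, because not stated: two-sided 5%, a continuous outcome at one visit, all 45 analysed, and the correlation r between covariate and outcome.

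**The plan's own figure.** Specific Aim 2 gives 80% power at d = 0.76. Without a covariate, the noncentrality is 0.76 / √(1/30 + 1/15) = 0.76 / √0.1 = 2.403. With 43 df and critical t 2.017, power is 65.2%. The 80% is not reproduced for this sample. That is a separate matter and adds no weight here; 65.2% is simply the reference value.

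**With one baseline covariate.** Residual variance falls by the factor (1 − r²), one df is lost, and chance imbalance in the covariate inflates the variance by 1 + 1/41 on average:

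noncentrality = 0.76 / √[(1 − r²)(1/30 + 1/15)(1 + 1/41)], 42 df, critical t 2.018.

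At r = 0 this is 2.375; at r = 0.5 it is 2.742.

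| r | Power, adjusted | Change v 65.2% (points) | CI width v unadjusted |
|---|---|---|---|
| 0 | 64.1% | −1.1 | 1.01 |
| 0.2 | 65.8% | +0.7 | 0.99 |
| 0.3 | 68.2% | +3.0 | 0.97 |
| 0.4 | 71.6% | +6.5 | 0.93 |
| 0.5 | 76.4% | +11.2 | 0.88 |
| 0.6 | 82.6% | +17.5 | 0.81 |
| 0.7 | 90.1% | +25.0 | 0.72 |

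Break-even is r = 0.158. A simulation with 20,000 trials per value gave adjusted power of 64.2, 68.5, 76.6 and 90.1% at r = 0, 0.3, 0.5 and 0.7, against about 65% unadjusted.

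**With dropout.** At an assumed 21 v 10 (about 30% lost; the inflation factor becomes 1 + 1/27), unadjusted power is 48.1% and adjusted power at r = 0 is 46.6%. The worst case is then a loss of about 1.5 points, and break-even is about r = 0.20.

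**Which outcomes can benefit.** The following is illustration on assumed inputs: lognormal use with log SD 0.6 to 0.8, log-scale correlation 0.5 to 0.6, and 30 to 70% zeros after the quit attempt. Changes are in power points, all 45 analysed.

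| Covariate | Quitting unrelated to baseline use | Heavier users quit less (log-odds −0.5 per SD) |
|---|---|---|
| Outcome's own baseline measure | r 0.15 to 0.38; about 0 to +6 | r 0.34 to 0.49; +4 to +11 |
| Proxy correlating 0.5 with baseline use | r 0.08 to 0.18; −0.8 to +0.4 | r 0.16 to 0.24; about 0 to +1.5 |
| Cigarettes/day against all-or-none abstinence | r 0; −1.1 | r (absolute) 0.22 to 0.24; +1.1 to +1.4 |

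The case for adjusting is therefore best where the covariate is the outcome's own earlier value, and weak for a loose proxy or for abstinence outcomes.

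**The case against.** The strongest reply is that the plan contains no error. Randomisation makes the unadjusted comparison unbiased on average, its standard error already allows for chance imbalance, and the comparisons are exploratory in a pilot whose stated purpose is feasibility. All of that stands. It limits the point to an improvement in precision and sets its weight.

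A second reply is that the figures fit the planned analyses only loosely. They describe one continuous outcome at one visit with no dropout, whereas the plan has counts, a proportion and a binary outcome at three time points. That also stands; the figures show direction and rough scale.

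A third is that the benefit of fixing the covariate in advance is uncertain. Mobile CM Procedures refers to feedback from the first two cohorts, so those had run, and the documents do not say whether outcomes from the third had been seen. The benefit holds to the extent that they had not.

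A reader might also infer that baseline drinking is not collected, since Table 2 marks the Timeline Follow Back at the 6-month visit only. The documents do not support that: eligibility depends on past-month drinking, an alcohol history is taken and the AUDIT is given. That no drinks-per-week instrument is named is missing detail. What does remain open is whether a numeric weekly mean is kept for everyone, because a participant can qualify on one heavy occasion.

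**Conclusion.** The point holds as an optional, cheap improvement. The exploratory comparisons leave out baseline values that the trial already holds, at some cost in precision and none in bias. For 30 v 15, d = 0.76, two-sided 5% (assumed), one continuous outcome at one visit and no dropout, one covariate changes power from 65% to anywhere between 64% (r = 0) and 90% (r = 0.7).

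Three stronger readings are not supported. The gain cannot be called small, or large, because the documents give no correlation. The adjusted model should not lead for every outcome, because for abstinence outcomes and weak proxies the illustrative change is only about −1.1 to +1.5 points. Nor does adjustment justify the stated 80% power: that would need r of about 0.56, and the plan states neither a covariate nor a correlation.

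**What to change.** Add a short paragraph to Data Analyses:

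- **Cigarettes/day:** lead model is treatment plus baseline cigarettes/day from the smoking history questionnaire.
- **Drinks/week:** lead model is treatment plus screening drinks/week if recorded as a number for every participant, otherwise the baseline AUDIT score. Make this choice before outcome data are seen.
- For both, report the unadjusted estimate alongside.
- **Heavy episodes, proportion of days abstinent, days of smoking abstinence, drinking limits:** keep the unadjusted model as lead and give the adjusted estimate as a sensitivity analysis. For the binary drinking-limits outcome, report a risk difference obtained by standardisation, because adjusted and unadjusted odds ratios estimate different quantities.

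No new data are needed. The cost is one degree of freedom per adjusted model and, if the covariate does not predict the outcome, about 1 point of power with all 45 analysed or about 1.5 at an assumed 21 v 10. For the two lead models, that risk is greater if drinks/week has to fall back on the AUDIT.
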